# 5.1.5.5 Hospitalization/Death

In addition to the main secondary outcome defined by the rate of non-access hospitalizations or death, the rates of the following additional hospitalization related outcomes will be obtained and compared between the treatment groups:

a) Rate of access hospitalizations

b) Rate of all hospitalizations or death FHN Nocturnal Protocol Version 3.3: October 15, 2008 c) Rate of cardiovascular hospitalizations or death.

# 5.1.5.6 Vascular Access Events

Vascular access events will be tracked for both study endpoints and for safety. All vascular access procedures, including both inpatient and outpatient procedures, will be tracked on a monthly basis using a modification of the HEMO Study form 6. Vascular access procedures will include angioplasty, stenting, use of thrombolytics in fistulas or gortex grafts, removal of a permanent access (and reason for removal) and placement of a new permanent access.

## 5.1.5.7 Treatment Burden and Experience with Nocturnal Hemodialysis

The primary assessment of treatment burden will be based on the question: "How long does it take you to recover from a dialysis session in minutes?" This question was asked as part of a "Dialysis Symptom and Fatigue" questionnaire given to patients participating in the London Daily/Nocturnal HD Study [Heidenheim, 2003]. The other components of the "Dialysis Symptom and Fatigue" questionnaire had previously been validated [Lindsay, 1994] and were part of a battery of established QOL tools used in the London Study. The investigators of the London Daily/Nocturnal HD Study have reported that this question was successfully answered on 313 of 314 occasions. This single question instrument was positively correlated with subscales evaluating fatigue, disease stress, and psychosocial stress, and was negative correlated with the SF-36 physical and mental component summary scores. The instrument also had a high test-retest correlation of r = +0.86 over a 3-month time interval. The London Daily/Nocturnal HD Study indicated large reductions in recovery time were observed on both the daily and nocturnal dialysis therapies after patients switched to these therapies from conventional 3 times per week dialysis. This question will be asked at baseline, months 4 and 12.

## 5.2 Adverse Events

An adverse event is the appearance or worsening of any undesirable sign, symptom, or medical condition occurring after randomization into the study, even if the event is not considered to be related to enrollment into the study. Medical conditions/diseases present before enrollment in the study are only considered adverse events if they worsen after enrollment into the study. Abnormal laboratory values or test results constitute adverse events only if they induce clinical signs or symptoms, are considered clinically significant, or require therapy.

An unanticipated adverse device effect is any serious adverse effect on health or safety or any lifethreatening problem or death caused by, or associated with, a device, if that effect, problem, or death was not previously identified in nature, severity, or degree of incidence in the investigational plan or application (Including a supplementary plan or application), or any other unanticipated serious problem associated with a device that relates to the rights, safety, or welfare of subjects."

All adverse events must be recorded on the Adverse Events Form (Form 307) with the following information:

- a) The severity grade (mild, moderate, severe)
- b) Relationship to the study drug(s) (suspected/not suspected)
- c) Duration (start and end dates or if continuing at final exam)
- d) If it constitutes a SAE, a Serious Adverse Events Form (Form 308) should be completed. A serious adverse event is defined as an event which:

- a) Is fatal or life-threatening
- b) Results in persistent or significant disability/incapacity
- c) Constitutes a congenital anomaly/birth defect
- d) Is medically significant, i.e., defined as an event that jeopardizes the patient or may require medical or surgical intervention to prevent one of the outcomes listed above
- e) Requires inpatient hospitalization or prolongation of existing hospitalization, unless hospitalization is for:
  - i) Routine treatment or monitoring of the studied indication, not associated with any deterioration in condition
  - ii) Elective or pre-planned treatment for a pre-existing condition that is unrelated to the indication under study and has not worsened since the start of study drug
  - iii) Treatment on an emergency outpatient basis for an event not fulfilling any of the definitions of a SAE given above and not resulting in hospital admission
  - iv) Social reasons and respite care in the absence of any deterioration in the patient's general condition.

#### 5.3 Potential Risks of Nocturnal Hemodialysis

Studies in nocturnal home hemodialysis patients thus far have not identified significant complications of the procedure. Surveys conducted for this study among the principal investigators for each Clinical Center in this consortium have not identified an increased risk of vascular access failure, or of complications from either hypokalemia or hypophosphatemia. We speculate that the low rate of access complications is due to self-cannulation of the dialysis access by the patient, a decreased incidence of dialysis hypotension and the daily use of heparin. Appropriate monitoring of serum electrolytes, with appropriate adjustments of the dialysate, has been successful in minimizing the risk of electrolyte abnormalities. Less is known about the effects of nocturnal home hemodialysis on secondary hyperparathyroidism and bone metabolism. These and other potential adverse effects that have not yet been identified will need to be monitored during this study and details of this monitoring are provided below.

In addition, there is a risk that there will be either a disconnection of the blood tubing or at the vascular access site, or a leak from the dialysis machine. A number of monitoring systems will be in place to detect these problems. All patients on nocturnal dialysis will use enuresis sensors to detect blood leaks at the needle site. Interlink® devices will be used to secure catheter connections and mesh will be used to secure the needles and lines of patients using grafts or fistulas for dialysis access. Floor sensors will be used to detect fluid leaks from machines and lines. [Lockridge, Jr., 2001] Except where patients are monitored on a routine basis, all nocturnal home dialysis patients will need to have a home partner who can assist with any alarms that may occur during the hemodialysis treatment.

The protocol for monitoring other potential complications is noted below.

a) Vascular Access Complications: Access infection, stenosis, thrombosis, and intervention will be defined, and a detailed protocol developed to monitor and treat these complications in both groups. The primary measure of vascular access complications will be primary unassisted patency rate (time to first access intervention). Groups will also be compared with respect to: number of access interventions per patient years, time to first thrombosis related access failure, and number of thrombosis related access failures per patient years,

number of access infections per patient years, number of infection related access failures per patient years, time to first infection related access failure.

- b) Iron Losses: Patients on daily hemodialysis have been shown to have increased iron losses compared with conventional patients. Iron utilization will be documented in both groups.
- c) Malnutrition: Although it is anticipated that nutritional status will improve with nocturnal hemodialysis, the potential for malnutrition exists. There may be increased dialytic losses of amino acids due to increased clearances provided with nocturnal hemodialysis. Thus, nutritional status, as outlined in Sections 5.1.3.3 and 5.1.5.3, will be monitored on a regular basis.
- d) Patient Burn-Out: Patient fatigue is a potential concern with the increased frequency of treatments with nocturnal hemodialysis, especially with the requirement that the patients perform the dialysis treatments themselves. The proportion of patients who require a change in dialysis modality lasting more than 2 weeks (back to conventional hemodialysis or to peritoneal dialysis) will be assessed along with reasons for modality change.
- e) Calcium and phosphorus balance: Nocturnal hemodialysis is known to decrease serum phosphate and even lead to hypophosphatemia. Persistently low serum phosphate may lead to weakness, osteomalacia and severe hypophosphatemia (defined as a serum level < 1.0 mg/dl) may cause hemolysis, acute respiratory failure, myocardial depression, or seizures. In addition, nocturnal hemodialysis can lead to negative calcium balance due to calcium loss through ultrafiltration. This may lead to increase of PTH and alkaline phosphatase. These laboratory parameters will be monitored on a regular basis as outlined in Section 3.4.1.d.

#### 6. Data Collection and Monitoring

#### 6.1 Frequency of Measurements

For those patients who were randomized in version 2.1 of the protocol to the conventional in-center hemodialysis arm of the study, they will be given a choice to either continue with conventional incenter HD three times per week or convert to conventional home hemodialysis three times per week. For all these patients, data will continue to be collected as indicated in version 2.1 of the protocol regardless of whether they convert to home hemodialysis. That is, the main data collection periods will be at 5 months of follow-up and 14 months of follow-up and the schedule for data collection in protocol version 2.1 will be followed. Baseline data that can be obtained by chart review only for the newly added second baseline visit will also be entered into the database. This data will likely consist only of baseline laboratory data.

All patients who were randomized under version 2.1 of the protocol into the conventional in-center arm of the study will need to sign a new consent form for the revised protocol. For all patients who consent to the study with the version 3.0 or higher protocol, data will be collected as summarized in Table 9.

For those patients who were in baseline at the time of the protocol change, the period for baseline was extended from 12 weeks to 24 weeks for all baseline variables except for the two co-primary outcomes of the change in Left-Ventricular Mass by Cine-MRI and the change in SF-36 Physical Health Composite Score. For these two co-primary outcomes, the data will need to be obtained no more than 12 weeks prior to randomization; otherwise the measurement(s) will need to be repeated. Each of these patients will need to sign a consent form for the revised protocol prior to the

resumption of data collection. Those baseline data collection items that do not result in patient burden (e.g., routine lab test data, chart review data) can be updated at the discretion of the clinical center prior to randomization.

Most questionnaires (including HRQL, depression, cognitive function, and treatment burden) and objective tests of physical function will be performed at baseline, and at 4 and 12 months post-randomization. The purpose of the 4-month (F4) assessment is to allow evaluation of short-term effects prior to significant attrition, while the 12-month (F12) assessment is intended to allow evaluation of longer-term effects. The cardiac cine-MRI will be performed at baseline and 12 months (B, F12) only.

Kinetic modeling sessions will be performed twice in the baseline period and monthly after randomization through month 12. Kinetic modeling parameters, including information on the dialysis prescription and the pre- and post-dialysis concentrations of urea, creatinine, and phosphate, as well as pre-dialysis albumin will be obtained at each session, while other labs will be collected less frequently (see Table 9 B). The pre- and post-dialysis blood pressures, post-dialysis weight, and the presence of intradialytic hypotensive episodes will also be obtained for the kinetic modeling session. Twice during baseline and monthly during follow-up, start and end times, pre- and post-dialysis blood pressures, and pre- and post-dialysis weights will be retrospectively obtained for the one-week interval preceding the modeling session, generally including two additional dialyses (for a total of six dialyses, including the modeling session) in daily patients. In addition, information on the dialysis prescription (but not local laboratory measurements) will be recorded for quality control for one of the dialyses during the second week follow-up randomization.

The frequency of local laboratory measures other than those described above for basic kinetic modeling will depend on the frequency with which they are performed at the various Clinical Centers, and should follow DOQI clinical practice guidelines. Locally performed pre-dialysis hemoglobin, calcium, bicarbonate, potassium, and sodium should be recorded at baseline and at least once per month post-randomization, while ferritin, transferrin saturation, and parathyroid hormone should be recorded at baseline and at least once every 3 months. Only baseline values performed less than 3 months before randomization will be used for any analysis.

All prescribed medications will be recorded at baseline and at months 4, 8, and 12 during follow-up.

Adherence to therapy will be obtained at baseline and on a monthly basis. All events, such has hospitalizations, deaths, access procedures, and discontinuations will be monitored continuously throughout follow-up.

The baseline kinetic modeling sessions are designated as "B" visits and are numbered sequentially. The follow-up visits are designated as F1 (month 1), F2 (month 2), and so on through the F12 visit.

# 6.2 Details on Measurements

# 6.2.1 Cardiac MRI

The cardiac MRI will be performed at baseline and at the month 12 visit. The most commonly used method to measure LVM is two-dimensional (2D) Doppler echocardiography. Since the method assumes a geometric shape of the normal heart, it is less accurate for dilated or extremely hypertrophic hearts. Furthermore, the results are heavily operator dependent and the variability of the measurement for LVM was found to be wider than originally thought [Collins, 1989;Palmieri,

1999]. Cine-MRI has been shown to be more accurate and less volume and operator dependent than 2D-echocardiography. In addition to determination of LVM, the cine MRI technology allows for measurement of various cardio-dynamic parameters, such as end-diastolic volume (EDV), end-systolic volume (ESV), stroke volume, ejection fraction, myocardial mass and cardiac output [Kramer, 2004]. We believe that the relative superiorities of MRI over echocardiography are compounded in ESRD patients who not only have a high prevalence of LVH, but who also suffer from volume expansion between dialysis sessions [Stewart, 1999].

Cine-MRI assessment of LVM showed a good interstudy reproducibility of 7.8 g (mean weighted values from 11 studies), intraobserver reproducibility of 4.8 g, and interobserver reproducibility of 9.0 g in mainly normal subjects. This is contrasted by a mean weighted interstudy SD for 2D-echo of 19.2 g [Myerson, 2002]. For these reasons cardiac cine MRI will be used for the assessment of LVM in all study patients.

Availability of MRI centers experienced in performing standard cine-MRI examinations has been verified by the Clinical Centers using a standardized questionnaire. MRI scans will be performed at designated MRI centers close to each patient's study dialysis unit. Scans will be digitized and provided to a Cardiac Core MRI reading center where they will be analyzed in a standardized way by a trained person, blinded to the patient's treatment allocation.

### 6.2.2 Home Blood Pressure Readings, Dialytic Blood Pressure, Interdialytic Weight Gains, and Intradialytic Hypotensive Episodes

Home blood pressure readings will be obtained at baseline and at months 4 and 12. Home blood pressure will be measured using the Omron HEM-705CP blood pressure monitor which meets the standards of the Association for the Advancement of Medical Instrumentation. This device is capable of storing 28 measurements and has been extensively used in research. Calibrated devices will be distributed to the Clinical Centers. Subjects will be trained on its use with a published protocol [O'Brien, 2001]. Study subjects will take 12 home self blood pressure measurements during a 48-hour midweek interval and an additional 12 home blood pressure measurements on the weekend. Subjects will also be asked to bring their medication to the study Clinical Center for their scheduled visits. Blood pressure measures will be taken at least two hours after a dialysis session, or one hour prior to a dialysis session. The start and end times of any dialysis session during the 2-day measurement session will be noted.

Pre and post-dialysis systolic and diastolic blood pressures, the nadir recorded intradialytic systolic and diastolic blood pressures, pre and postdialysis weights, and the presence of intradialytic hypotension requiring intravenous saline will be recorded from the HD run sheets for each HD session over a 1-week interval prior to and including the kinetic modeling session once during baseline and at months 4, 8 and 12 during follow-up. Interdialytic weight gains will be calculated from the pre and post weights. See Table 11 C.

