## **Phosphate**

Phosphate binder dosage will be tapered, as clinically indicated, during the first one to two months of nocturnal home hemodialysis therapy. Increased phosphate intake should be strongly advised before dialysate phosphate addition is considered. The decision should be based on the initially weekly and then monthly pre / post dialysis laboratory values. Patients should not add phosphate into the dialysate during the first dialysis after a night off.

Since no commercially available dialysate additive phosphate preparation is available, Fleet® enema or Fleet® phosphosoda (oral) containing sodium phosphate have been used. They can be added into the bicarbonate or the 'acid' concentrates if bicarbonate cartridges are used. The addition of 30 ml of Fleet® enema yields a dialysate phosphate concentration of about 1.2 mg/dL or 0.4 mmol/L. Changes in the amount of phosphate are usually in the range of 20-30 mL of Fleet® enema. A usual dose is 30 to 80 mL or more. The oral Fleet® phosphosoda solution is more concentrated and is added in volumes of 15 mL, 30 mL or 45 mL or more. Some patients have complained of itchiness at the higher dose but this is not uniform. As sodium phosphate results in increased dialysate sodium concentration of 137 mEq/L can be used if increased thirst or hypertension is observed.

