levels in hemodialysis patients, which decline during dialysis treatments and increase between treatments. Due to these variations in blood pressure level in association with the dialysis treatment schedule, it is possible that a comparison of blood pressures in patients on a 6 times per week intervention vs. patients on a 3 times per week intervention may yield different results depending on the timing of the blood pressure measurements in relation to the dialysis treatments.

Two strategies will be used to address these issues. First, in both treatment arms the primary assessment of blood pressure level will be based on the average of a sequence of 12 home blood pressure readings obtained over a mid-week 2-day period obtained in the home and the average of 12 home blood pressure readings obtained over a weekend 2-day period obtained in the home.(see Section 6.2). Blood pressure readings are obtained mid-week and on the weekend in order to capture the potential difference in blood pressure readings that may occur on the weekend due to the longer interdialytic interval. The protocol for the home blood pressure readings should avoid bias from white-coat effects, and by averaging over multiple times points is intended to minimize confounding due to factor (c). Second, rather than designating a single main blood pressure outcome, the effects of the interventions on the hypertension domain will be evaluated based on three different outcomes related to changes in blood pressure over time. In addition to the 48-hr home blood pressure measurement protocol, pre- and post-dialysis blood pressures and the use of antihypertensive medications will be recorded at baseline, and then at months 4, and 12 during follow-up. As described in Section 9.11, the effects of the interventions will be evaluated primarily based on three different outcomes: i) the change from baseline to 12 months in the 48-hour average systolic blood pressure, ii) change from baseline to 12 months in the number of antihypertensives prescribed, and iii) change from baseline to 12 months in the proportion of patients with 48-hour average pre-dialysis systolic blood pressure less than 110 mmHg.

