## 6.2.3 Bioelectric Impedance

Single frequency bioelectric impedance (BIA) assessments should be performed at baseline and at months F4, and F12 visits. BIA is not required on randomization. All measurements should be conducted in the recumbent position, and should be performed immediately prior to a mid-week HD treatment (i.e., Wednesday or Thursday) and after at least two consecutive dialysis treatments for patients in the nocturnal arm of the study. BIA is not required for patients with bilateral amputations or who have metallic implants such as a pacemaker.

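### The second set of home blood pressure readings is meant for the longer interdialytic interval but is fixed to the calendar weekend, which matches that interval only for some dialysis schedules

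*Protocol*

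**What the plan says.** Section 5.1.4.1 (Hypertension Domain) states that "in both treatment arms the primary assessment of blood pressure level will be based on the average of a sequence of 12 home blood pressure" values taken mid-week, together with "the average of 12 home blood pressure readings obtained over a weekend 2-day period obtained in the home". The reason it gives for the weekend block is a possible difference in pressure "that may occur on the weekend due to the longer interdialytic interval". The change in average home systolic pressure from baseline to 12 months is the first of three outcomes named there for the domain. The same section warns that the comparison of arms may depend on when readings fall relative to dialysis, and relies on averaging to limit this.

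Section 6.2.2 puts this into practice by calendar. The first set is "12 home self blood pressure measurements during a 48-hour midweek interval"; the second set is "an additional 12 home blood pressure measurements on the weekend". Readings must be at least two hours after a session or one hour before one. Session start and end times in the measurement period are noted.

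Dialysis days are not fixed. Section 3.1.2 leaves the conventional prescription otherwise open. Section 6.2.3 times bioimpedance "immediately prior to a mid-week HD treatment (i.e., Wednesday or Thursday"), which fits both a Monday/Wednesday/Friday and a Tuesday/Thursday/Saturday pattern. For the nocturnal arm, the phosphate instructions in section 3.4.1 d) acknowledge the night off ("Patients should not add phosphate into the dialysate during the first dialysis after a night off") but no section assigns it to a particular night.

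**The concern.** The purpose is defined by the dialysis cycle and the rule by the calendar. They coincide only when the long gap falls on Saturday and Sunday. Otherwise the weekend block samples wholly or partly ordinary intervals, so the same 24 readings represent different parts of the cycle in different patients. That is the timing dependence section 5.1.4.1 sets out to limit.

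The protocol ties other measures to the cycle. Section 5.1.5.1 c) records weight gain over 48 and 72 h intervals in the conventional arm and 24 and 48 h intervals in the nocturnal arm. Section 6.2.3 requires at least two consecutive treatments before bioimpedance in the nocturnal arm. At stake is the precision and interpretability of the home pressure measure in the hypertension domain.

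**Working it through.** **1. The plan's own intervals (Table 4).** Medians: three sessions of 3.5 h and six of 7.0 h per week.
- Maximum gap: 72 − 3.5 = 68.5 h conventional; 48 − 7.0 = 41.0 h nocturnal.
- Average gap: (168 − 3 × 3.5)/3 = 52.5 h; (168 − 6 × 7)/6 = 21.0 h.

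All four match Table 4.

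**2. Share of a Saturday 00:00 to Sunday 24:00 window inside the long gap.** Weekdays and start times are assumptions: conventional starts 07:00 to 18:00, nocturnal starts 22:00 to 23:00.

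| Schedule | Hours of 48 | Share |
|---|---|---|
| Mon/Wed/Fri | 48 | 100% |
| Tue/Thu/Sat: 48 − (start + 3.5) | 26.5 to 37.5 | 55 to 78% |
| Nocturnal, Saturday off | 41 | 85% |
| Nocturnal, Friday off | 22 to 23 | 46 to 48% |
| Nocturnal, Sunday off | 18 to 19 | 38 to 40% |
| Nocturnal, Monday to Thursday off | 0 | 0% |

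With Sunday off, the overlap is only the first hours of the gap, which look like an ordinary day.

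**3. Mean hours since dialysis.** Assumed readings at 08, 10, 13, 16, 19 and 22 h on each day, dropping those excluded by the two-hour/one-hour rule. The mid-week block is Tuesday-Wednesday or Wednesday-Thursday, and the two block means are weighted equally (also an assumption).

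Sessions ending at noon:
- Mon/Wed/Fri weekend: Saturday sum 160, Sunday sum 304, 464/12 = 38.7 h. Mid-week: (160 + 21)/9 = 20.1 h. Combined: (38.7 + 20.1)/2 = 29.4 h.
- Tue/Thu/Sat weekend: (21 + 160)/9 = 20.1 h. Mid-week 20.1 h. Combined 20.1 h.
- Difference: 29.4 − 20.1 = 9.3 h.

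Sessions ending at 18:00:
- Mon/Wed/Fri weekend: (124 + 268)/12 = 32.7 h. Mid-week: 249/10 = 24.9 h. Combined 28.8 h.
- Tue/Thu/Sat weekend: 24.9 h. Mid-week: 24.9 h (Wednesday-Thursday) or 32.1 h (Tuesday-Wednesday). Combined 24.9 to 28.5 h.
- Difference: 0.3 to 3.9 h.

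Nocturnal, 23:00 to 06:00:
- An ordinary day sums to 52, so an ordinary block averages 104/12 = 8.7 h. A block holding the day after the night off averages (52 + 196)/12 = 20.7 h.
- If either block catches that day: (20.7 + 8.7)/2 = 14.7 h. If neither does: 8.7 h.
- Difference: 6.0 h.

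**4. What equal pooling does once the second block is tied to the long gap.** The comparison is with the mean over all eligible reading times in the week.
- Conventional, 18:00 endings, block at the end of the gap (Sunday-Monday for Mon/Wed/Fri): (268 + 197)/10 = 46.5 h; pooled (46.5 + 24.9)/2 = 35.7 h. Weekly mean 1087/36 = 30.2 h. Excess 5.5 h.
- Conventional, noon endings, same block: (304 + 21)/9 = 36.1 h; pooled (36.1 + 20.1)/2 = 28.1 h. Weekly mean 847/33 = 25.7 h. Excess 2.4 h.
- Nocturnal: pooled 14.7 h. Weekly mean (6 × 52 + 196)/42 = 12.1 h. Excess 2.6 h.

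With later sessions, re-anchoring and then pooling equally over-weights the late gap more in the conventional arm.

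**The case against.** The strongest reply is that the measure uses 24 readings, not 12. Some weekday nights off are caught by the mid-week block: Monday and Tuesday nights by a Tuesday-Wednesday block, Tuesday and Wednesday nights by a Wednesday-Thursday block. If nights off were spread evenly over the week, four of seven would give 14.7 h and three 8.7 h, an average of 12.1 h, equal to the true weekly mean. This stands. It rules out a demonstrated net distortion in the nocturnal arm, but not the spread between patients.

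All patients dialyze three times weekly during training (section 2.8), so randomization balances baseline schedules in expectation, and the model in section 9.5 adjusts for the baseline value. Part of the difference in cycle between arms is the treatment itself. These points stand too.

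The stakes are limited. Hypertension has no single main outcome, and section 5.1.1 lists pre- and post-dialysis pressures among its key measures. Session times are recorded and the analysis plan, which is not shown, may use them. Recorded times allow adjustment but cannot supply long-gap readings that were never taken.

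A reader might infer a bias in favour of nocturnal dialysis, or a shift of 2 to 4 mmHg. The latter comes from applying an assumed rise of 1 to 2 mmHg per 10 h to the weekend-only noon difference (38.7 − 20.1 = 18.6 h). The documents give no such slope. On all 24 readings the same slope gives about 1 to 2 mmHg for noon sessions and under 1 mmHg for evening ones. Nor do Tuesday/Thursday/Saturday patients miss the long gap: all of Sunday lies in it. Their weekend readings stop before its end, but so do those of Monday/Wednesday/Friday patients (58 h at most, against 68.5 h).

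**Conclusion.** The mismatch between purpose and rule holds. Sections 5.1.4.1 and 6.2.2 aim the second block at the longer interval but schedule it by calendar, and nothing in the protocol aligns the two. The consequence is avoidable schedule-related variation in the home pressure measure: up to about 9 h in mean time since dialysis between conventional schedules (0 to 4 h with evening sessions) and about 6 h between nights off.

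These figures rest on assumed weekdays, session times, reading times and equal weighting of the blocks. Only the Table 4 intervals and the two-hour/one-hour rule come from the protocol. A net direction of bias between arms is not established, and its size in mmHg cannot be derived. The co-primary outcomes and the power figures are untouched. The change is worth making because it is cheap, not because a treatment comparison is shown to be wrong.

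**What to change.** In sections 5.1.4.1 and 6.2.2, define the second 12 readings by the patient's own longest interdialytic interval of that week (nocturnal arm: the interval containing the night off). Take the first 12 in a 2-day period of ordinary intervals. Apply this at baseline and months 4 and 12. Two days can contain the 41.0 h nocturnal gap but not the 68.5 h conventional one, so state which part of the conventional gap is sampled and keep it the same for everyone.

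Analyse the two averages separately, or combine them weighted by each interval type's share of interdialytic time. At the Table 4 medians the long gap's share is 68.5/(168 − 10.5) = 43% conventional and 41.0/(168 − 42) = 33% nocturnal, against 50% under equal pooling. Weighting corrects fully only if the block represents the whole gap, so separate reporting is the safer default.

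The number of readings, the device, the visits and every dialysis schedule stay as they are. The cost is that reading days must be set for each patient at each assessment, using session times the protocol already has noted.
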